The Person-centered Care Assessment Tool (P-CAT) measures the extent to which an aged care setting is person-centered. The tool is primarily intended for use by staff but expanded with a version for the older person's self-reporting. The Swedish version of the P-CAT has been found to be valid, reliable, and applicable for further use (Edvardsson *et al.* 2010, Sjögren *et al.* 2012). Person-centered care is increasingly regarded as being synonymous with best quality care. In this project, both the staff version and the version for the older will be used.

The Person-Centered Climate Questionnaire: The Person-centered Climate Questionnaire exists both in a patient and a staff version. The instruments have been shown as being a valid and reliable contribution for assessing to what extent the climate of care environments is person-centered. The factors are safety, everydayness and hospitality. The instrument enables descriptions and comparisons of environments, exploration of correlates between person-centeredness and patient outcomes and/or measure results of various interventions (Bergland *et al.* 2015, Edvardsson *et al.* 2013).

The newly developed self-reported questionnaire was named Next of Kin Participation in Care (NoK-PiC): Before the start of this project, there was a complete lack of instruments designed to measure the participation of next of kin in palliative care in nursing homes. To deal with this, a questionnaire for next of kin's participation was developed before the beginning of the project. Literature reviews of previous research about the next of kin's participation was performed including all types of care in general as well as focus on palliative care and the care at nursing homes. The systematic literature review resulted in a questionnaire with 36 items about next of kin's participation in palliative care. The new questionnaire was psychometrical tested on 400 next of kin (Westergren et al. 2020).

Experiences of palliative care: The staff will also answer a questionnaire with 47 items, newly constructed to capture changes in health professionals' attitudes, knowledge and assessment of the quality of palliative care; before (one month's), and after finishing the implementation intervention. Validation of the questionnaire is ongoing (Östlund et al. 2014).

Focus group interviews and individual interviews

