Official title of the study:
Implementation of Knowledge-Based Palliative
Care for Frail Older Persons in Nursing Homes

NCT number: NCT02708498

Date of the document: April 8, 2015, updated October 6, 2020

Statistical Analysis Plan

Simple descriptive statistics:

Median-Mean, Quartiles, Percentage

These are applied to all quantitative studies.

Baseline study:

Target population: Older people

Instruments: Characteristics of older participants, WHOQOL-BREF & WHOQOL-OLD

The data were analysed in one descriptive and one analytical section. In the descriptive section, numbers and percentages were calculated on a group level. A mean score was calculated for each domain using both the raw domain score, a standardized domain score (SDS) with the raw domain score divided by the number of items in the domain (1-5) and a transformed domain mean score (TDS 0-100) according to the instrument manuals. The different calculations were performed to enable comparison of our results with those from other studies.

In the analytical section, the participants were divided into two age groups (66-88 years and 89-102 years) by the population median age and gender (female and male). To examine differences in quality of life, a comparison of medians was conducted using the Mann-Whitney U test.

Comparative studies (Baseline and Follow-up):

Target population: Older people, next-of-kin, staff

Instruments: PCAT, PCQ-S, PCQ-P, WHOQOL-BREF, WHOQOL-OLD, Your experience of palliative care, Next-of-Kin Participation in Care (NoK-PIC)

The selection of the statistical tests to analyze data other than the descriptive statistics was based on whether the data were distributed normally and the scale level of the instruments. The Mann-Whitney U-test and the Kruskal-Wallis test was applied to compare the baseline characteristics of the two groups. The quantitative data collected from questionnaires were analyzed using within-group comparisons (the data from after the intervention period were compared with the data from before the intervention period in the intervention group and the control group) by Wilcoxon signed rank test.

Either Pearson's chi-square test or Fisher's exact test was used when the expected value was less than 5.

A two-tailed p-value of <0.05 was regarded as statistically significant.

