In order to investigate if the drop-outs consisted a threaten of external validity we performed sub-groups analysis through comparing the drop-outs in the intervention group with the participants in the intervention group, and comparing the drop-outs within the control group with the participants in the control group.

Analyses were performed using IBM SPSS Statistics version 24.

Logistic regression studies (Baseline and Follow-up):

Target population: Staff
Instruments: P-CAT, PCQ-S

A univariate logistic regression analysis was performed with the independent variable improvement/non-improvement in P-CAT and PCQ-S and the dependent variable group (control/implementation).

Psychometric studies

Target population: Next-of-kin
Instrument: Next-of-Kin Participation in Care (NoK-PiC)

Step 1. Dimensionality

The dimensionality of the 37 items was explored by means of Rasch Model Analysis (RMA) and Explorative Factor Analysis (EFA). EFA needs complete data, i.e. no missing responses in any items. RMA can process missing data. Estimation methods merely summarize the non-missing observations that are relevant, and compare them with their expectations.

NoK-PiC data was analysed according to Rasch Measurement Theory (RMT), using the polythomous Rasch model in RUMM2030 (Professional Edition 5.4). A principal component analysis of the residuals was conducted in RUMM2030 to explore dimensionality of the NoK-PiC items. Person location estimates were derived from subsets of items that loaded positively and negatively on the first principal component of residuals. The overall proportion of persons with significantly different measures from the two item subsets should be <5% to support unidimensionality.

EFA was conducted based on recommendations including parallel analysis to decide for decision about how many factors to retain for rotation, Minimum Rank Factor Analysis (MRFA, that is able to estimate the percentage of common variance explained by the EFA model), and on a promine rotation that allows factors to correlate (oblique). In addition, since the items are polythomous, and since MRFA assume only minor departures from normality, we based the analysis on a polychoric correlation matrix. The software FACTOR (Lorenzo-Seva, Ferrando, release 10.5.03, June 2017) was used to conduct EFA.

Step 2. Item reduction

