Based on conceptual reasoning among the researchers and based on RMA item reduction was conducted. The main statistical reasons for item reduction was based on item fit. In general, individual item fit residuals should range between -2.5 and 2.5, with the ideal being 0. Signs of multidimensionality/under discriminating items (fit residuals >2.5) and local dependency/item redundancy/over discriminating items (fit residuals > -2.5) led to further exploration of the possible reasons for misfit. This exploration included inspection of item residual correlations, and the item characteristic curves to get a graphical understanding of the deviations from Rasch model expectations. The nature of observed misfit (local response dependence or multidimensionality) often needs to be determined based on conceptual reasoning rather than statistics.

Step 3. Dimensionality after item reduction

Dimensionality of the remaining 30 items (after step 2) was explored using EFA, following the same procedures as described above (Step 1). The appropriateness of performing EFA was, in this step, checked according to quality criteria, i.e. by means of: the Kaiser-Meyer-Olkin Measure of Sampling Adequacy (should be KMO 0.50 or above); and Bartlett's test (should be p-value <0.05).

Step 4. RMA of final and separate factors

According to RMA, a set of items, supposed to be unidimensional, rated (dichotomous or polytomous scoring) in a sample, are compared to the "Perfect Rasch Model" that is based on fundamental measurement principles from the physical sciences. The model separately locates persons and items on a common interval level logit metric, ranging from minus to plus infinity, with mean location set at zero. The extent to which a successful measurement has been achieved is determined by examining the fit between observed data and model expectations. If data accord sufficiently with the model, linear measurement and invariant comparisons are possible. However, almost no scale is perfect, thus "almost perfect" can be a goal to achieve. Here the RMA addresses targeting, reliability, model fit, Differential Item Functioning (DIF, by gender and age), and hierarchical item ordering.

Step 5. Group comparisons

The IBM SPSS Statistics 23 software was used for comparisons between independent groups. Data were assessed regarding underpinning assumptions, described, and analysed using Mann Whitney U-tests. Significance was set to $P < 0.05$.

Target population: Next-of-kin

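### The NoK-PiC unidimensionality cut-off of 5% equals the chance rate of nominal 5% person tests and leaves no room for sampling error

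*SAP*

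**What the plan says.** The rule is in the SAP under Psychometric studies, Step 1 (Dimensionality), for the NoK-PiC. After a principal component analysis of the Rasch residuals, "Person location estimates were derived from subsets of items that loaded positively and negatively on the first principal component of residuals". The two estimates are compared person by person, and "The overall proportion of persons with significantly different measures from the two item subsets should be <5% to support unidimensionality".

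Step 1 does not give the significance level of the person tests, the size of loading that puts an item in a subset, the number of persons, or any interval for the proportion. A level of 0.05 appears elsewhere. Under Comparative studies, "A two-tailed p-value of <0.05 was regarded as statistically significant", and Step 5 of the psychometric section uses the same level for group comparisons. For sample size, the Protocol's section on questionnaires states: "The new questionnaire was psychometrical tested on 400 next of kin".

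The rule is not used alone. Step 1 also runs an exploratory factor analysis (EFA), with parallel analysis to set the number of factors. Step 2 reduces items on item fit and conceptual reasoning, and says that the nature of misfit "often needs to be determined based on conceptual reasoning rather than statistics". Step 3 re-examines the 30 remaining items by EFA.

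**The concern.** A person test at 5% comes out significant for about 5% of persons even when both item subsets measure the same thing. Requiring the observed proportion to be below 5% places the cut-off at its own null expectation. Whether a sound scale passes then depends largely on sampling variation.

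The stake is how the dimensionality of the NoK-PiC is reported. In Step 1 this is the only explicit numerical pass/fail criterion for unidimensionality, and the NoK-PiC is listed among the instruments for the comparative studies. A proportion of 5% or slightly more could be reported as evidence against a single scale when it is what chance predicts.

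**Working it through.** The plan gives no error rate for this rule, so there is no figure to reproduce.

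**Inputs**
- Cut-off: proportion below 5% (SAP, Step 1).
- n = 400 next of kin (Protocol, questionnaires). The SAP gives no n for the Rasch step, so other values are shown as a range.
- Person-test level: two-sided 5%. This is an assumption carried over from other SAP sections.
- Persons independent, with a common null rate p.

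**Rule as written.** Let X be the number of significant persons, X ~ Bin(n, p). The rule fails when X/n ≥ 0.05. At n = 400 that means X ≥ 20, and the expected count at p = 0.05 is also 400 × 0.05 = 20. The standard deviation is √(400 × 0.05 × 0.95) = 4.4 persons.

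P(X ≥ 20 | n = 400, p = 0.05) = 53.2%.

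Other n at p = 0.05: 56.4% (n = 100), 54.5% (n = 200), 44.5% (n = 401, where 21 are needed), 52.3% (n = 800).

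**Interval rule.** Call unidimensionality unsupported only if the exact (Clopper-Pearson) 95% lower limit exceeds 5%. The limit is the 0.025 quantile of Beta(x, n − x + 1). At n = 400, x = 29 gives 4.91% and x = 30 gives 5.12%, so 30 persons are needed.

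| True rate p (n = 400) | Fails as written (X ≥ 20) | Fails interval rule (X ≥ 30) |
|---|---|---|
| 3% | 2.0% | <0.1% |
| 4% | 18.3% | 0.1% |
| 5% | 53.2% | 1.9% |
| 6% | 82.8% | 12.5% |
| 7% | 95.8% | 37.5% |
| 10% | >99.9% | 96.4% |

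At n = 200 the interval rule needs 17 persons. False rejection at 5% is 2.4% and detection of a true 10% is 79%.

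**Is the null rate really 5%?** The subsets are chosen from the same residuals, so it need not be. Unidimensional polytomous Rasch data were simulated with 37 items, 4 categories, 400 persons, 60 replicates per setting, known item parameters, weighted-likelihood person estimates and |t| > 1.96. Two person distributions were used: mean 0 with SD 1, and mean 0.5 with SD 1.5. The documents give none of these settings except the 37 items and the 400 persons.

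| How the subsets are formed | Person rate | Scale fails rule as written |
|---|---|---|
| Random halves | 3.5–3.8% | 8–10% |
| Loadings beyond ±0.3 | 3.9–4.9% | 23–53% |
| Sign of loading only | 7.5–8.5% | 98–100% |

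The last row is the literal reading of Step 1. At person rates of 7.5% and 8.5%, P(X ≥ 30) is 53% and 79%, so the interval alone does not restore control under that split.

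**The case against.** The strongest reply is that nothing in the SAP hangs on this rule alone. Step 1 describes exploration by two methods. The number of factors is assigned to EFA with parallel analysis, item reduction to item fit and conceptual reasoning, and the later dimensionality check to EFA only. No action is stated for failing the 5% rule, and no outcome score is tied to it. This stands. A reader might infer that the rule decides whether the NoK-PiC is reported as one scale or split, and so which scores enter the comparisons. The documents do not say so.

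The second reply is that failure about half the time is not an established property of the procedure. This also stands. The figure needs an exact 5% null rate. Step 1 states no person-test level, and the simulated failure rates ran from 8% to 100% at n = 400, depending on how the subsets are formed.

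The third reply is that a confidence interval is no cure if the data-driven split raises the null rate. It stands too, and it changes the fix. A reader might also assume that the test is repeated on the final scales, but Step 4 does not name it among the properties examined.

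None of this removes the defect. The criterion has no allowance for sampling error, and its level, subset rule and n are unstated. Being exploratory lowers the consequence without making the proportion interpretable.

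**Conclusion.** The concern holds in a limited form. If the person tests run at two-sided 5%, the cut-off sits at the chance expectation. With an exact 5% null rate and n = 400, a truly unidimensional NoK-PiC fails about 53% of the time. The figure is sensitive: about 18% at a true null rate of 4%, about 83% at 6%, and close to 100% in the simulated sign-of-loading split. It rests on an assumed test level, independent persons and the Protocol's n.

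The effect is confined to the psychometric component. The rule informs the reported structure beside EFA and conceptual reasoning, and it governs no comparison between intervention and control. The correction is worth making because it is cheap and because failing the present rule says little about the scale.

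**What to change.** Amend Step 1 to:

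- state the person-test level (two-sided 5%), the loading rule that forms the two subsets, and n;
- report the count and proportion of significant persons with an exact binomial 95% confidence interval;
- treat unidimensionality as unsupported by this test only if the lower limit exceeds 5%;
- note that the calibration is nominal, because choosing the subsets from the same residuals can raise the null rate above 5%. A reference rate simulated from the fitted unidimensional Rasch model could replace 5%.

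The SAP describes this work in the past tense, so the change can be made as a reporting correction. The cost is a few sentences of SAP text and an interval from counts already produced. The simulated reference rate is optional and needs some extra computing, but no new data.

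The downside is less sensitivity to mild multidimensionality. At n = 400, detection of a true 10% falls from nearly 100% to about 96%, and of a true 7% from about 96% to about 37%. At n = 200, detection of a true 10% is about 79%.

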The seminar groups will be led by two experienced clinical nurses and researchers from the field of palliative care and geriatric care. The participants in the seminar groups will reflect together over the content of the developed binder of educational material and will relate it to their own work in order to identify areas suitable for changes and/or development. These areas will also be identified based on the Swedish Register of Palliative Care (SRPC). The knowledgebase for discussions in the seminar groups is seven selected quality indicators out of the total of 27 questions concerning essential aspects of palliative care. The seven quality indicators are: Prevalence of pressure ulcers, documented individual prescription when needed of opioid and anti-anxiety drugs, oral health assessment, talks about the substance and direction, pain analysis and regular estimation of pain intensity and regular use of instrument for symptom assessments.

The evaluation of the implementation

Data collection is made before and after the implementation, same time for intervention- and control groups. The implementation of the educational intervention will be evaluated by using qualitative and quantitative methods (see Table 2).

Table 2. Sub studies and data collection i Kronoberg County and Skåne County 2015 and 2016 for the implementation of knowledge based palliative care.

Subjects	Method	Selection in the implementation nursing homes	Selection in the control nursing homes*
Sub study 1: Older persons	Structured interview (based on WHOQOL-BREF (26 items), WHOQOL-OLD (24 items), P-CAT (13 items) and The Person-Centered Climate Questionnaire (17 items)	20 older persons were interviewed before and after three months after finished implementation	The same as for the implementation nursing homes
Sub study 2: Next of kin	Qualitative interviews participation and structured interview WHOQOL-BREF (26 items), WHOQOL-OLD (24 items)	20 next of kin before and three months after finished implementation	20 next of kin before and three months after finished implementation
Sub study 3: Next of kin	The participation of next of kin in palliative care at nursing homes (36 items) WHOQOL-BREF (26 items), WHOQOL-OLD (24 items)	100 next of kin before and after nine months	100 next of kin before and after nine months
Sub-study 4:	Psychometric study; test-retest, explorative factor analysis	See above	See above

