Instrument: WHOQOL-BREF

Data were analyzed using IBM SPSS Statistics 20 and IBM SPSS Amos, version 25. In a first step, WHOQOL-BREF's negatively phrased items (Q3, Q4, and Q25) were reversed (1=5, 2=4, 3=3, 4=2, 5=1). Two items – question 1, about overall QOL, and question 2, about the overall perception of health – were analyzed separately.

Validity

Internal validity in terms of data quality and targeting was assessed by missing values, item response, and floor and ceiling effects. Floor and ceiling effects were calculated and should be less than 20% in order to ensure that the scale is capturing the full range of potential responses in the population and that changes over time can be detected. The Kolmogorov-Smirnov test was used to assess normality at the item level. A statistically non-significant result ($p \geq 0.05$) indicates normality. Construct validity was estimated by correlating item/question 1: "How would you rate your QOL?" and item/question 2: "How satisfied are you with your health?" with the four domains in the WHOQOL-BREF using Spearman's rank correlation.

Reliability

Internal consistency was assessed using Cronbach's alpha. To determine to which degree each item correlates with the total score, Corrected Item-Total Correlations (CIT) were calculated. The limit for satisfactory item correlation was set to > 0.30 . Values less than 0.30 indicate that the item is measuring something different from the scale as a whole.

Factor structure

The appropriateness of performing CFA was checked according to quality criteria. These criteria were fulfilled by means of the Kaiser-Meyer-Olkin Measure of Sampling Adequacy (0.90, should be 0.50 or above); Bartlett's test (0.01, should be < 0.05); and determinant (0.008, should be > 0.00001). The number of cases per item was also calculated. Recommendations range from 2 to 20 subjects per item, with an absolute minimum of 100 to 250 subjects. Confirmatory Factor Analysis (CFA) was applied to assess goodness of fit by means of various descriptive fit indices. Specifically, the normed fit index (NFI), the comparative fit index (CFI) and the root mean squared error of approximation (RMSEA) were used.

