The NFI equals the difference between the chi-square of the two models divided by the chi-square of the null model. An NFI over 0.90 is preferable. An NFI of .90 shows that the model of interest improves the fit by 90% in relation to the null model. CFI assesses fit relative to a null model and ranges from 0 to 1, where values exceeding 0.95 are regarded as acceptable. The RMSEA test assesses the lack of fit per degree of freedom of the model. Zero represents a perfect fit, ≤ 0.05 indicates very good fit, $>0.05-0.08$ good fit, and ≥ 0.10 poor fit. IBM SPSS Amos only accepts data files with no missing values, and therefore, 14 participants were excluded from the CFA analysis (n=240).

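### WHOQOL-BREF factor analysis: with only a null-model comparator and no rule for combining indices, good fit cannot show that four domains are distinct

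*SAP*

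**What the plan says.** The point concerns the SAP, Psychometric studies, WHOQOL-BREF in next of kin, Factor structure. "Confirmatory Factor Analysis (CFA) was applied to assess goodness of fit by means of various descriptive fit indices", and the indices named are NFI, CFI and RMSEA. NFI should be over 0.90 and CFI over 0.95. For RMSEA, "Zero represents a perfect fit, ≤ 0.05 indicates very good fit"; above 0.05 up to 0.08 is good, and 0.10 or more is poor. NFI and CFI are both defined against a null model. No one-factor, second-order or other substantive rival is mentioned, and nothing says what to conclude if the three indices point different ways.

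The model being fitted is not named. Four domains appear only under Validity, where they are correlated with the two global questions.

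The SAP also prints results: "Kaiser-Meyer-Olkin Measure of Sampling Adequacy (0.90, should be 0.50 or above"), "Bartlett's test (0.01, should be < 0.05"), "determinant (0.008, should be > 0.00001"), and "14 participants were excluded from the CFA analysis (n=240").

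**The concern.** A confirmatory factor analysis of this instrument is useful mainly if it can tell four related domains from one general dimension. Indices that measure improvement over a model with no correlations at all do not address that. A model that groups correlated items in almost any sensible way will improve greatly on the null. When item correlations are modest, RMSEA is also compressed towards zero, so fixed bands become easy to meet.

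At stake is what the psychometric study may claim: that next of kin's answers support four distinct domains, when the planned evidence would look much the same if they did not.

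**Working it through.** **Inputs.** n = 240 and determinant 0.008 (SAP, Factor structure). The instrument is "WHOQOL-BREF (26 items") in Protocol Table 2. The question on overall quality of life and the one "about the overall perception of health – were analyzed separately" (SAP), which leaves 24 items. Not in the documents, so assumed: domain sizes 7/6/3/8, normal data, and a common inter-domain correlation φ, varied.

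**1. The SAP's own Bartlett figure.** χ² = −(n − 1 − (2p + 5)/6) × ln(det) = (239 − 53/6) × 4.828 = 1111 on 276 df, p about 1e-100. A p-value of exactly 0.01 would need a determinant of about 0.23. The printed 0.01 agrees with the printed determinant only if it means less than 0.01.

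**2. Null model.** χ² = 239 × 4.828 = 1154 on 24 × 23/2 = 276 df. RMSEA = √[(1154 − 276)/(276 × 239)] = 0.115. With all 26 items and n = 254 (240 + 14) it would be 0.104.

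**3. What each cut-off demands.** There are 24 × 25/2 = 300 variances and covariances. The four-factor model has 24 + 24 + 6 = 54 parameters, so 246 df; the one-factor model has 48, so 252 df. The χ² limit for a given RMSEA is df × (1 + 239 × RMSEA²).

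| Model | RMSEA limit | χ² limit | NFI there | CFI there |
|---|---|---|---|---|
| Four-factor | 0.05 | 393 | 0.66 | 0.83 |
| Four-factor | 0.08 | 622 | 0.46 | 0.57 |
| One-factor | 0.05 | 403 | 0.65 | 0.83 |
| One-factor | 0.08 | 637 | 0.45 | 0.56 |

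A CFI of 0.95 corresponds to an RMSEA of about 0.027, so the three criteria differ greatly in strictness.

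**4. NFI.** NFI above 0.90 needs χ² below 115. A correct four-factor model expects χ² near 246, so NFI near 1 − 246/1154 = 0.79 (median 0.78 in simulation). The chance that a correct model passes is about 6e-14.

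**5. If the truth is one dimension.** The one-factor model is the four-factor model with all six correlations equal to 1, so the four-factor χ² can never be the larger. With loadings set to reproduce the determinant, the four-factor model had RMSEA of 0.05 or less in about 100% of samples and CFI above 0.95 in about 95%. NFI above 0.90 failed in every sample, but it fails correct models too.

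**6. If the truth is four factors.** Share of 500 samples in which the wrong one-factor model passes, and in which the 6-df difference test (5% critical value 12.6) rejects it:

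| φ | RMSEA ≤ 0.05 | CFI > 0.95 | NFI > 0.90 | Rejected by difference test |
|---|---|---|---|---|
| 0.5 | 3% | 0% | 0% | about 100% |
| 0.6 | 50% | 0% | 0% | about 100% |
| 0.7 | 95% | 6% | 0% | about 100% |
| 0.8 | 100% | 46% | 0% | about 100% |
| 0.9 | 100% | 84% | 0% | 54% |

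At φ of 0.4 or below no sample had RMSEA of 0.05 or less. Equal domain sizes (φ 0.5 to 0.8) and loadings varied by 20% gave nearly the same results. When the truth was one factor, the difference test rejected one factor in about 7% of samples, close to its nominal 5%.

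**7. Dependence on the determinant.** Taking 0.0008 as a sensitivity assumption, the one-factor model has RMSEA of 0.05 or less in 1% of samples at φ = 0.6 and 24% at 0.7. At 0.00008 the figures are 0% and 1%. Expected NFI for a correct model stays below 0.90: 1 − 246/(239 × 7.131) = 0.86 and 1 − 246/(239 × 9.433) = 0.89.

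**The case against.** The strongest reply is that the SAP does not judge structure by RMSEA alone. It lists three indices with cut-offs, and no wrong one-factor model met all three in simulation. CFI by itself rejected the wrong model in at least 94% of samples up to φ = 0.7. This stands: the documents do not support inferring that the plan rests on the RMSEA bands. But NFI contributes no discrimination, since it fails right and wrong models alike. Anyone who supports a structure must set it aside, and the SAP gives no priority between CFI and RMSEA once that is done.

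A reader might also infer that the bands call a wrong model very good as a general matter. That depends on domain correlations the documents do not give, and on a determinant that sits awkwardly with the other printed figures. In simulations matched to that determinant, a KMO of 0.895 or more was almost absent at φ up to 0.6, and occurred in 2–4% of samples at 0.7 and 20–28% at 0.9. The printed 0.90 therefore points either to high domain correlations, where CFI weakens too, or to a smaller determinant, where RMSEA is less lenient. The documents cannot settle which.

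Two further readings go too far. One is that the structure is untested: it is tested against the null model, only not against a simpler structure. The other is that the WHOQOL-BREF outcomes hang on this analysis: the SAP's Baseline study section scores domains according to the instrument manuals, and nothing makes scoring conditional on the factor analysis.

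**Conclusion.** The concern holds in limited form. As planned, the fit indices cannot show that four domains are distinct. If the items formed one dimension, a four-factor model would still pass the RMSEA and CFI cut-offs in about 100% and 95% of samples, and the NFI cut-off would fail whatever the truth. The RMSEA part follows from nesting and does not hang on the exact determinant.

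The companion result, that a one-factor model can reach RMSEA of 0.05 or less when four factors are true, is conditional. It needs domain correlations of about 0.6 or more and the determinant as printed, and it rests on assumed domain sizes and normal data.

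The scope is the next-of-kin psychometric study. Domain scoring and the before–after comparisons do not depend on it. The point is worth correcting because the change is nearly free and the intended claim is not otherwise supported.

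**What to change.** - Name the model that the confirmatory factor analysis fits, with its items and domains.
- Fit a one-factor model to the same 240 cases. Claim support for four distinct domains only if both the chi-square difference test (6 df) and CFI favour the four-factor model.
- State how the indices combine when they disagree. Do not rely on the NFI cut-off or on the RMSEA bands alone, and report the null-model RMSEA beside the fitted one.
- Report the estimated inter-domain correlations. At about 0.9 the difference test rejects one factor only a little more than half the time, so a non-significant result should be read with them in view.
- Check the printed determinant and Bartlett figures against the output, and write the latter as an inequality if that is what was meant.

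The cost is one additional model on existing data and a few sentences in the SAP and the report.
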